#### Modifications during the COVID-19 outbreak:

To address the public health concerns during the outbreak of COVID-19, the initial telephone eligibility screening and pre-treatment assessment will be modified to include precautions to safeguard Veterans' health during the outbreak. The phone screen will be conducted as described, and will be modified to include working with interested and eligible Veterans to establish the VA Video Connect option for the pre-treatment assessment. The pre-treatment assessment will be modified as follows: prior to the pre-treatment assessment appointment a research assistant will send two copies each of the IRB-approved informed consent form and HIPAA authorization form via mail, along with a pre-addressed, pre-stamped envelope for the participant to return their signed informed consent form and HIPAA authorization form to the research staff at the Syracuse VAMC. The mailed packet will also include copies of the response options for some of the baseline questionnaires as well as an information sheet with relevant phone numbers for VA behavioral health services and crisis resources including the Veterans Crisis Line. At the appointment, the assessors will follow standard VA Video Connect procedures to create a confidential medical virtual room. At the beginning of the appointment, the assessor will verify the participant's current location and phone number to ensure if any disruptions occur, we can re-contact the Veteran and provide assistance. During the informed consent process, the participant will be able to reference the paper copy of the informed consent and HIPAA authorization forms and the assessor will visually show materials within the virtual medical room. All research staff will be trained in standard VA Video Connect procedures and follow the same suicide risk protocol that we established for our other in-person and telephone appointments (which matches how video connect behavioral health appointments are being conducted). Research staff will have the participants hold up the signed consent and HIPAA forms to take a screenshot of the signatures and stamps, which will be saved in password-protected files in the study folder on the approved VA server to which only IRB-approved research staff will have access. Participants will be asked to send back the signed informed consent and HIPAA authorization within the self-addressed envelope. If the paper copies of the consent and HIPAA are not received quickly, research staff will work with participants to obtain signed paper copies before the end of the study, with the screenshots of the signed forms as back-up documentation. Research staff will also print the images of the signed consent and HIPAA forms and attach them to the new paper copies in the event that there is a significant delay or new copies are sent to the participant to sign. All consents and authorizations will be stored in the same locked file cabinets and the same rooms as usual. All other appointments will occur via telephone, which is already an option in our standard protocol. At the pre-treatment assessment and all follow-up assessments, we will also administer 10 items related to the experience and impact of COVID-19 and related social isolation/quarantine recommendations. There will be one additional COVID-19 item given only at the post-treatment assessment regarding the impact of COVID-19 on their experience of the study intervention.

Treatment-as-Usual (TAU). All participants will be encouraged to maintain appropriate TAU for their co-occurring condition(s) as recommended by their VA treatment providers. This means that they may be receiving psychotherapy and/or medication management as often as the VA treatment providers deem necessary. This can include treatment within the primary care teams, through behavioral telehealth, and/or specialty outpatient mental health. We will monitor the participant's engagement in TAU throughout the study.

All Participants, in addition to having access to TAU for co-occurring conditions, will also be allowed to use pharmacotherapy for insomnia provided that they have begun such treatment prior to enrollment. Medication use will be tracked on the sleep diaries. Changes in sleep medication use will not be precluded after the post-treatment assessment has been completed, but will continue to be tracked via sleep diaries and medication usage questions at follow-up assessments. Other sleep treatments for insomnia (e.g. CBT-I for participants in the SH condition; mindfulness based CBT-I for those in the CBT-I condition) will be precluded until after the post-treatment assessment. Utilization of non-pharmacologic insomnia treatments between the post-treatment and subsequent assessments will be monitored and recorded at follow-up assessments. Finally, all participants will be asked to complete sleep diaries for the duration of the intervention period and one week prior to the follow-up assessments. Capturing medication and other treatment data will allow us to examine whether they confound study intervention treatment effects.

Sleep Hygiene (SH) Participants will participate in four individual sessions over the telephone that will last 15-30 minutes each across a 6-week time period. Guided by a manual and patient workbook (see Appendices),

interventionists will guide patient through SH material (i.e., basic psychoeducation about sleep, discuss SH factors that disrupt and improve sleep, set SH goals, develop action steps to achieve those goals). At each session, participants will complete three items from the PHQ-9 (items for depressed mood, anhedonia, and suicide/death ideation) to monitor mood and suicide risk over the course of treatment. This data may also be used for research purposes. Sessions will be audiotaped for fidelity to SH principles.

CBT-I Intervention Participants will receive four individual sessions that will last approximately 15-30 minutes each across a 6-week time period. Some sessions may be conducted over the telephone. Following the manual and a patient workbook (see Appendices), CBT-I will consist of a standard, structured, multi-component CBT-I intervention used in previous studies by the PI's (sleep education, sleep hygiene, sleep restriction, stimulus control, and cognitive therapy). At each session, participants will complete three items from the PHQ-9 (items for depressed mood, anhedonia and suicide/death ideation) to monitor mood and suicide risk over the course of treatment. This data may also be used for research purposes. Participants will also be given sleep diaries at each session to fill out for the next appointment. Sessions will be audiotaped for fidelity.

Patient Treatment Adherence. Participant adherence will be monitored by homework logs, which participants complete each session. Daily sleep diaries, which are used to guide the refinement of the sleep restriction component of CBT-I, will also be used to monitor adherence. Rates of participation and adherence will contribute to our assessment of feasibility and acceptability.

Therapists & Therapists Training. [name] will train at least one PC-MHI provider at each site to deliver efficacious CBT-I therapy in a manner consistent with the VACO CBT-I Training model. Training includes individual and group face-to-face didactics, independent reading, role-playing, and supervised training cases until competency is met. A similar procedure will follow for SH training. [name] will provide direct clinical supervision and [name] will meet bi-weekly with therapists along with [name] and [name] in group supervision to review cases.

Therapist Treatment Fidelity. Implementation science research emphasizes the importance of assessing fidelity to evidence-based treatments shown to be efficacious in highly controlled settings. We will assess fidelity by audio taping intervention sessions (securely stored on a VA server) and use reliable fidelity measures developed in our pilot study to rate therapist fidelity. Our measures reflect two core components of therapist fidelity: 1) Adherence to the intervention manual content, and 2) Competence in the delivery of the intervention (i.e., quality). These two components are important to measure because a therapist may demonstrate high levels of adherence (that is, provides the treatment content as described in the manual), but does so in a manner that demonstrates low levels of competence. Thus, the treatment would be delivered in a manner that is "rote," poorly timed or insensitive to the individual patient. The converse may also occur: low adherence and high competence. Both scenarios would compromise conclusions about the outcomes of the treatment study. Therefore, it is critical to measure both components of therapist fidelity in an intervention trial.

Follow-Up Assessments (5 in total) will occur at post treatment (6 weeks), and every 6 weeks until the 6 month follow-up (at week 30) using most questionnaires used at the pre-treatment assessment (see **Table 1**). The initial follow-up assessment will be completed in person, with the option to conduct them over the phone if necessary. All other follow-up assessments will occur by phone unless face-to-face is requested by participants. If a participant misses a follow-up, we will send a letter (see missed follow-up letter template) to help facilitate rescheduling the follow-up.

Assessors for all assessments will be blinded research staff who have completed training in human subjects research and in specific research activities (recruitment, screening, informed consent, assessments, qualitative interview skills, and data management) via a didactic series of independent reading, lecture and role play.

An Exit Interview will occur immediately following the post-treatment assessment and be conducted by a trained and blinded interviewer. It will consist of both self-report instruments and a semi-structured interview to assess treatment feasibility and acceptability of CBT-I (participants in CBT-I condition only) and attitudes towards psychotherapy for co-occurring conditions (all participants).

### Measures

Screening/Eligibility Measures will include: review of the electronic medical record; the PHQ-9 to assess for the presence of SI; an unpublished instrument that we have developed and used in prior work the *Demographic & Veteran Information Form* to capture basic demographic and military service information; the STOP-BANG sleep apnea questionnaire; an unpublished instrument the *Health Behaviors Interview* to screen any drug or substance use over the past 3 months; *MINI International Neuropsychiatric Interview (MINI)* modules for

mania and psychosis, medical chart review to assess current enrollment in inpatient/partial hospitalizations, medications, and specific exclusionary diagnoses; and as noted in eligibility criteria, the *ISI*, *PHQ-9*, and *PCL* will be used.

**Outcome Measures.** The Scale for Suicidal Ideation (SSI) is an interview that measures the “intensity of the patient’s specific attitudes, behaviors, and plans to commit suicide.” Participants will be asked about “current” SI, defined as occurring during the past week (SSI-C), at pre-treatment and each subsequent time point. The SSI is considered the gold standard measure for SI with good internal consistency, construct validity, and predictive validity, is sensitive to change over time, and has been used with Veterans. The SSI-C will be our primary SI severity outcome.

In addition, each assessment will include: several instruments administered for screening (*ISI*, *PHQ-9* and *PCL*); the 20-item *Beck Hopelessness Scale* (BHS); a one week sleep diary to ascertain total sleep time, sleep efficiency variables, the frequency and intensity of nightmares and medication use; the *Suicide Attempt Self-Injury Interview (SASII)* to assess suicidal behaviors.

Table 1. Measures	Screen	Pre	Post	12 wks	18 wks	24 wks	30 wks
Insomnia Severity Index (ISI)	X	X	X	X	X	X	X
Scale for Suicidal Ideation (SSI)		X	X	X	X	X	X
STOP-Bang Sleep Apnea Questionnaire	X						
Demographic and Veteran Information Form		X					
MINI IntNatl Neuropsychiatric Interview (MINI)		X					
Non-VA Treatment Questionnaire		X					
Health Behaviors Interview		X					
PTSD Symptom Checklist-DSM 5 (PCL-5)		X	X	X	X	X	X
Patient Health Questionnaire (PHQ-9)		X	X	X	X	X	X
Beck Hopelessness Scale (BHS)		X	X	X	X	X	X
Contemplation Ladder		X	X	X	X	X	X
Columbia-Suicide Severity Rating Scale (CSSR) subscale		X	X	X	X	X	X
COVID-19 Items		X	X	X	X	X	X
Suicide Attempt Self-Injury Interview (SASII)		X	X		X		X
Sleep Diary (with nightmare items)		X	X	X	X	X	X
Treatment Engagement Assessment			X	X	X	X	X
Semi-Structured Exit Interview			X				
Two measures of Treatment Attitudes		X	X				
Electronic medical Chart Review		X	X				X

**Feasibility, Acceptability, and Treatment Receptivity Measures** will be collected/administered at the Patient Exit Interview using a mixed methods approach as follows. A *Sleep Diary* is completed upon awaking and used to guide the sleep restriction portion of CBT-I; it will also be used to measure treatment adherence (an aspect of feasibility) with respect to sleep scheduling. Two instruments with high reliability, the 10-item *Attitudes Toward Seeking Professional Psychologist Help* and the 19-item *Thoughts about Psychotherapy Survey* will be administered both at baseline and at the exit interview to assess attitudes toward psychological care.

*Semi-Structured Interviews* will be conducted by a trained research interviewer to gather: (1) additional participant feedback about acceptability, facilitating factors, and obstacles to CBT-I engagement (feasibility) from CBT-I instruments and (2) feedback from all participants on attitudes toward PTSD and depression treatment. The Interviewer will use a written guide (see “Exit Interview” in Appendices) to conduct the ~15-30 minute interviews, which includes a protocol for engaging the respondent and establishing rapport, questions and topics that need to be covered during the conversation, the order of inquiry, and prompts for follow up questions. Interviewers follow the guide but are able to pursue topical trajectories in the conversation that may stray from the guide when appropriate to fully understand respondents’ comments and to enrich the data. The interviewer records responses in writing, however, sessions will be audiotaped for consensus on themes.

We will assess therapist perspectives on the feasibility and acceptability of delivering CBT-I to veterans with suicide ideation in primary care using a Provider Survey. We will also include items enquiring about therapists’

experiences participating in the study (e.g., burden, benefits). A *Provider Survey* to gather therapist perspectives on feasibility/implementation factors will take place at study conclusion.

Therapist Fidelity. We will code therapy audio tapes using reliable fidelity measures (See Appendices) developed in the pilot study. Coding will be conducted by a team of coders trained to criteria, who will rate both adherence and competence such that sessions 1 or 2 **and** sessions 3 or 4 will be rated for each subject. Thus, 2 sessions for will be rated for fidelity in each case. We will also double code 20% of cases to assess inter-rater reliability. *Adherence measures:* there is one measure for each of the four CBT-I treatment sessions each with a unique range of scores (e.g., Session 1 range = 0-23). Scores for overall adherence for a given session can be captured by raw scores and by transforming the total number of points earned into a “percent of content delivered” score. Given that adherence items code the presence or absence of events, measuring internal consistency is not appropriate. A reliable *Competence measure* will be used to assess quality of CBT-I treatment delivery, comprised of 4 items (pacing/focus, language, therapeutic stance, tailoring treatment) scored on a 3-point scale (1=needs work, 2=satisfactory work, 3=good work); total range of 4-12. For the SH intervention, we will code a similar number of sessions, and use nearly identical *Adherence* and *Competence* measures, but in the case of Adherence, we will be coding to make sure only SH elements, and not other CBT-I elements, are delivered.

Site-based factors that may impact implementation will be assessed through data collection on each of the three study sites including: therapist factors (e.g., training/degree; CBT-I and/or sleep treatment experience; years of experience in primary care; years in current position; full/part time status), and site factors (e.g., rural/urban; number/FTE providers; patient population; turnover; number of EBTs provided; patient acuity). We will consider how these factors vary across sites and how they are associated with fidelity and outcomes.

### Data Analysis and Statistical Considerations

General Considerations. A check of randomness will be conducted for each baseline demographic, meditational, and outcome variable collected using standardized bias estimates. Any estimate greater than .15 will be controlled for statistically in subsequent analyses.

Power Analysis Considerations. Mixed effect analyses will be used to examine the effects of CBT-I on the developmental trajectories of the primary outcomes of interest; insomnia, depression, PTSD, and SI severity. Here, the power approach for longitudinal mixed effects models put forth by Hedeker, et al. was used. This tests for the statistical power to detect change over time (i.e., slope) using a random effects model (both slope and intercept). For the current proposal, necessary estimates were supplied via pilot results examining unconditional change in SI, depression, PTSD, and insomnia. In all instances, we are interested in the effect of CBT-I on the linear slope (the five time points after the intercept time point) using a two-sided alpha of .05 and .80 power, a 1:1 group ratio, no correlation between intercept and slope, and no correlated residual variance. Higher correlations between intercept and slope and among residual variance both serve to increase power estimates. To help improve power to detect change, two additional data collection time points have been added to this revised proposal. For the outcomes of SI, depression, and insomnia severity, pre-post (6 weeks) standardized effect sizes from the pilot study were all positive and exceeded .40. For power simulations, we tested for linear change from baseline through 6 month follow-up (time points 0, 6, 12, 18, 24 and 30 weeks), testing for the power to detect an effect size of .4 at the 30 week (6 month follow-up) time point. A 20% attrition rate was incorporated into the model, assuming a typical longitudinal attrition pattern with most participants lost early (7% at post-treatment and 5%, 3%, 3%, and 2% at subsequent assessments, respectively). Remaining estimates were supplied via pilot results examining unconditional change in SI, insomnia, depression, and PTSD. For the main outcome of SI, pilot data using the C-SSRS suggests an intercept variance of 10, slope variance of 1.2, and residual variance (error variance) of 24. With these estimates, 240 participants are required to achieve .80 power. Fewer participants are required to achieve .80 power to detect linear change for the remaining outcomes (N = 223 for depression, N = 222, for insomnia, and N= 184 for PTSD) with intercept, slope and residual variances based on pilot data.

For the main SI outcome, power likely improves with the change to the SSI as we suspect that more variance in this instrument will be captured in the model tested, resulting in less residual variance and a smaller residual variance/slope variance ratio. Both are important components of statistical power to detect change in mixed effects models.

For the structural equation model to be tested, the logic of MacCallum, Browne, and Sugawara was followed. This approach allows for the testing of a null hypothesis of not good fit, reversing the role of the null hypothesis

in conventional tests of model fit, so that a significant result provides strong support for good fit. This approach also allows for an estimate of power, where effect size is defined in terms of a null and alternative value of the root mean square error of approximation fit index. Here, adequate power ( $> .98$ ) to reject a hypothesis of close fit ( $RMSEA > .08$ ) with 136 degrees of freedom (a degrees of freedom of 136 is a somewhat conservative estimate as models including more covariates would provide more degrees of freedom), given a population  $RMSEA$  of  $.05$  was obtained. That is, if the true value of  $RMSEA = .08$ , and we test the hypothesis that  $RMSEA \leq .05$ , power is  $> .98$  for rejecting the hypothesis of close fit in the population. Additionally, adequate power ( $.98$ ) to reject a hypothesis of not-close fit ( $RMSEA \geq .05$ ) was also obtained. If model fit is actually extremely good ( $RMSEA < .01$ ), and we test the hypothesis that fit is not close, we have over  $.95$  power to reject the null hypothesis that  $RMSEA \geq .05$ .

With respect to Exploratory Aims, the number of participants likely to complete CBT-I represent a considerable sample with which to conduct fidelity assessments and to identify qualitative themes and the overall sample size offers the ability to explore quantitative data related to participant attitudes.

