### **Methods**

#### **Design Overview**

The proposed study is a multi-site, randomized, clinical trial conducted in a real world setting while collecting implementation data in a Hybrid I design. This study is designed to test the effectiveness of a brief, primary-care based form of CBT-I in a sample of Veterans (N=240) endorsing SI, insomnia, and co-occurring depression or PTSD. Following an initial telephone screening, all patients who agree to participate and who meet all initial inclusion criteria will be asked to participate in the study and to schedule a full baseline assessment. Eligible Veterans will then be randomized to one of two conditions: (1) CBT-I or (2) Sleep Hygiene (SH). All participants will be encouraged to maintain appropriate treatment as usual for their co-occurring condition(s) as recommended by their VA treatment providers. Comprehensive assessments will occur at pre-treatment (baseline), post-treatment (6 weeks), and every 6 weeks until a 6-month follow-up assessment (at 30 weeks).

**Randomization** will occur following informed consent and the subsequent pre-treatment assessment on a 1:1 ratio, stratifying on site, gender and current psychotherapy for depression/PTSD treatment. We will use a stratified block design with block sizes of six. As discussed in the analytic strategy, we will assess for equal distribution of other covariates of interest.

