As noted in the *Preliminary Data* section, our HSRD-funded pilot study recruited and randomized 54 participants over 8 months from the Canandaigua site alone. In this application we are proposing to enroll 320 participants to randomize 240 participants over 30 months (8 per month) from three sites (2-3 per month per site). In other words, although the target recruitment rate is slightly higher than in the pilot study, we are adding two additional recruitment sites (the Buffalo and Syracuse VAMCs) for this larger trial.

The initial eligibility screen will occur by telephone and be conducted by research assistants trained in this procedure following a written screening script; any Veteran may request to be seen in person. During the initial assessment, the research assistant conducting the screening will describe the study and all aspects of consent to the patient and evaluate comprehension of consent using two comprehension questions (see phone screen script). Following verbal consent, patients will be asked to verbally complete: the Insomnia Severity Index (ISI), sleep apnea screening questions, and a suicide assessment. The screening is constructed so as to avoid inviting Veterans to the intake assessment who are highly unlikely to meet eligibility criteria (e.g., due to the presence of sleep apnea or absence of insomnia). Participants meeting initial eligibility criteria who wish to participate will be scheduled for a baseline (pre-treatment) assessment.

We are requesting a waiver of consent documentation for this phone screening; full written informed consent will take place at the pre-treatment assessment for those participants who are eligible following the phone screen and wish to participate in the pre-treatment assessment.

If the participant is ineligible to participate in our study or is eligible for other studies, we would like to be able to ask them if they are interested in hearing about other research studies going on at their local VA if they are interested in participating. If interested, we would help connect that participant and the research team with them to obtain additional information.

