Upon completion of the initial eligibility screen and scheduling of the pre-treatment assessment, research staff will ask Veterans whether they currently receive VA payments via EFT (e.g., travel reimbursement) or via Direct Express debit card. For those Veterans not currently enrolled in EFT or the Direct Express debit card, research staff will inform the Veteran on the information required for enrollment in EFT or the Direct Express debit card and that the appropriate form will be provided during the in-person pre-treatment assessment. Once the Veteran completes the enrollment paperwork, it will be immediately turned over to the Syracuse VA or Canandaigua VA agent cashier.

If there are any issues with enrollment or receipt of compensation, research staff will contact the Veteran over the phone or the Veteran may call the research staff to communicate about the issues and work toward a resolution. Since this often requires a lot of information to be conveyed over the phone (i.e., research staff contacting the fiscal office for information for the Veteran) a follow-up letter with this information may also be sent to the Veteran in order to assist in the resolution of the payment issues. No identifiable data or sensitive payment information will be included with these payment letters.

The pre-treatment assessment will be conducted by assessors immediately following an informed consent process. The assessment will consist of self-report instruments described in the Measures section below. Participants who remain eligible will then be randomized (stratified by gender, study site and treatment status). Following informed consent and enrollment in the study, research staff will enter a study initiation note into the participant's electronic medical chart. This note will notify other VA providers, including the patient's primary care provider, only that the Veteran is participating in the study and receiving an intervention for sleep. Research staff will also enter progress notes into the participant's chart following completion of assessment sessions to document any suicide risk. A study completion note will be entered into the participant's chart

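### The Aim 1 slope test does not name the stratification factors (site, gender, current psychotherapy), the Aim 2 model omits psychotherapy, and the .15 balance rule will almost never add them

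*Combined protocol and SAP*

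**What the plan says.** - **Randomisation.** Design Overview describes allocation "stratifying on site, gender and current psychotherapy for depression/PTSD treatment", and adds: "We will use a stratified block design with block sizes of six". Procedures repeats the same three factors: "Participants who remain eligible will then be randomized (stratified by gender, study site and treatment status". Design Overview also says that "we will assess for equal distribution of other covariates of interest", which suggests that the stratifiers are themselves regarded as covariates.
- **General covariate rule.** General Considerations, under Data Analysis and Statistical Considerations, calls for standardised bias estimates on baseline demographic, mediational and outcome variables. It then says: "Any estimate greater than .15 will be controlled for statistically in subsequent analyses".
- **Aim 1.** The Data Analysis text specifies a mixed model with random intercept and slope and tests the CBT-I effect on both. No covariate is named for that test. The sentence on effect sizes lists gender, race, ethnicity and medication use. Site and psychotherapy are not named for Aim 1.
- **Aim 2.** The covariate list covers gender, age, minority status, site, baseline clinical scores and concomitant medications. Current psychotherapy is not on it, although the exploratory attitudes analysis is restricted by baseline psychotherapy status.
- **Related text.** On site-level factors, Measures says: "We will consider how these factors vary across sites and how they are associated with fidelity and outcomes". The treatment-as-usual text in Procedures says that medication and other treatment data will allow confounding to be examined. Neither puts a stratifier into a test model.

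**The concern.** An analyst who follows the text literally could fit the Aim 1 slope test without the factors the trial randomises by. Stratification makes the treatment estimate less variable to the extent that those factors predict rate of change. A model without them still counts their contribution as noise, so the reported standard error exceeds the true one, and confidence intervals and p-values are conservative.

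The .15 rule does not repair this. It admits a variable only when it is imbalanced, and stratified blocks are there to prevent imbalance. It will therefore select unstratified variables by chance and pass over the stratifiers. Since it is worded for demographic, mediational and outcome variables, site and psychotherapy may not be screened at all.

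The text is also ambiguous. The means used for effect sizes come from the fitted model, so gender, race, ethnicity and medication use may be in the test model or may not. Two analysts could fit different Aim 1 models and both claim to follow the plan.

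**Working it through.** **Inputs from the plan.** N = 240, 1:1, two-sided alpha .05, and effect size .4 at week 30 (Power Analysis Considerations). SI variances: "intercept variance of 10, slope variance of 1.2, and residual variance (error variance) of 24". Attrition of 7%, 5%, 3%, 3% and 2% gives retention of 1, .93, .88, .85, .82 and .80. Strata: 3 sites × 2 genders × 2 psychotherapy states = 12, in blocks of six. About 20% women (Study Population). Sites are taken as about equal, from "from three sites (2-3 per month per site".

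**Assumptions.** The plan does not give the unit of the slope variance, the standardising SD, the share in psychotherapy, or the share *f* of true slope variance that the factors explain. I score time 0 to 5 in six-week steps and use the model SD at week 30. I take 20–50% in psychotherapy and *f* = 0 to 20%.

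**1. The plan's own figure.** SD at week 30 = √(10 + 1.2 × 25 + 24) = √64 = 8. Slope difference = .4 × 8 / 5 = .64 per step. Generalised least squares with the stated attrition gives a slope variance term v0 = 3.0307. The standard error is √(4 × 3.0307 / 240) = .2247, and power is Φ(.64/.2247 − 1.96) = .813. The N for .80 power is 233, so the plan's 240 is reproduced within 3%.

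**2. Can the .15 rule bring the factors in?** For an unstratified variable the standard error of the standardised difference is √(4/240) = .1291. The chance of exceeding .15 in either direction is 2 × [1 − Φ(.15/.1291)] = .245, or .123 if only positive values count. For the stratifiers, 20,000 simulated trials per setting with 12 strata and blocks of six gave the chance that any is flagged:

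| In psychotherapy | Any stratifier above .15 |
|---|---|
| 20% | .0036 |
| 35% | .0010–.0014 |
| 50% | .0010 |

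A separate simulation put it at 2–4% with only 10% women, still rare.

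**3. Effect on the slope test.** Let v1 be the variance term with slope variance 1.2 × (1 − f), and r = √(v0/v1). Under perfect balance:
- type 1 error without the factors = 2 × [1 − Φ(1.96 r)]
- power without = Φ((.64/.2247 − 1.96) × r)
- power with = Φ(.64/√(4 v1/240) − 1.96)

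| f | v1 | r | Type 1 without | Power without | Power with | Gain (points) |
|---|---|---|---|---|---|---|
| 0 | 3.031 | 1.000 | .050 | .813 | .813 | 0 |
| 5% | 2.960 | 1.012 | .0473 | .8155 | .8216 | 0.6 |
| 10% | 2.889 | 1.024 | .0447 | .8184 | .8306 | 1.2 |
| 20% | 2.747 | 1.050 | .0395 | .8244 | .8487 | 2.4 |

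**4. Simulation under the actual blocking** (20,000 trials per setting). At f = 20%, the SD of the slope estimate is .218 without the factors and .215 with them, while the reported standard errors are .225 and .214. The loss is therefore in the reported standard error, hardly in precision.

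**5. Which terms are needed.** At f = 20%, main effects alone give type 1 error .040 and power .823. Adding by-time terms gives .049 and .847. At f = 0, the separate simulation put the power cost of the added terms at 0.2 point.

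**6. Time in weeks.** Data Analysis codes time as weeks. If the slope variance is also per week, base power is .836. Type 1 error without the factors is .045, .039 or .029, and the gain is 1.1, 2.2 or 4.3 points at 5%, 10% or 20%.

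**7. Should the .15 rule be dropped?** Simulation of 24,000 trials per setting used eight screened covariates, with shares now expressed as per-person slope variance (assumed):

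| Factors / each covariate | Rule only | Stratifiers only | Rule plus stratifiers |
|---|---|---|---|
| 5% / 2% | .829 | .832 | .844 |
| 5% / 5% | .873 | .829 | .885 |
| 5% / 0 | .807 | .830 | .820 |
| 0 / 2% | .824 | .807 | .823 |

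Entries are power. In the first row the SD of the estimate is .120 with the rule and .126 with stratifiers only, so a stratifier-only set can be less precise. A fixed set of all eight covariates plus the stratifiers gave .882 in that row.

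**The case against.** The strongest reply is that the effect is small and rests on an assumed quantity. If the factors explain only 2% of slope variance, the same formulas give power .8138 without them and .8162 with them. That gain of about 0.2 point is no larger than the simulated cost of the extra terms when the factors carry no information. There is also no shortfall against the plan: its variances come from unconditional change, so the .80 target already rests on the larger, unadjusted standard error, and the plan expects the switch to the SSI to help power. All of this stands, and it limits the point to a modest improvement.

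Keeping the .15 rule also leaves some conservatism. In the first row of the last table, type 1 error is .037 with the rule, .040 with the rule plus stratifiers, and .049 with stratifiers alone. When the screened covariates are uninformative, stratifiers alone do better. This also stands, and it favours a fully pre-specified set over a data-driven rule.

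For Aim 2, the model already controls for site, gender, baseline severity and medications. I have no calculation for adding psychotherapy there, so that part rests on consistency with the randomisation.

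The intentions to examine treatment confounding and site factors do not answer the point, since neither commits a test model to the stratifiers.

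**Conclusion.** The concern holds. The Aim 1 test names none of the three stratifiers, the Aim 2 list omits one, and the balance rule is a route that will almost never operate for them. This is incomplete specification with a small efficiency cost, and validity is intact: type 1 error is at or below nominal.

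If the factors explain 5–20% of true slope variance, the test runs at .047 to .040 instead of .05 and gives up 0.6 to 2.4 points of power, or up to 4.3 points if the slope variance is per week. If they do not predict slope, nothing is lost by omitting them. The size depends on the assumed share of slope variance and on the time unit; the direction does not. The correction is worth making because it is nearly free, and by the plan's own calculation SI needs all 240 participants for .80 power.

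**What to change.** 1. In every Aim 1 test model, name site, gender and current psychotherapy as main effects and by time. Main effects alone leave the slope test essentially unchanged.
2. Add current psychotherapy at baseline to the Aim 2 covariate list.
3. Keep the .15 rule as an addition. Replace it only with a pre-specified set that also holds the expected prognostic baseline variables.
4. State whether gender, race, ethnicity and medication use are in the Aim 1 test model or only in the effect-size calculation.
5. Say how a flagged baseline outcome score is handled. The natural reading is that the time-0 intercept covers it in its own trajectory model and it is not added there as a covariate.

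The cost is SAP wording, on variables already recorded in order to randomise. Aim 1 gains 4 main effects (site 2, gender 1, psychotherapy 1) and 4 by-time terms, 8 in all. That becomes 12 if the quadratic or a two-piece model is used, against 240 participants. Aim 2 gains one covariate. There is no added data collection or patient burden.
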